3.2. Study Procedures

Participants will have a screening visit and up to three scheduled clinic visits interspersed by two home intervals. The participants enrolled into the sub-study cohort will follow similar study procedures:

- ***Screening Visit (~2 hours):*** informed consent, potential Pure Tone Audiometry (air conduction audiometry), medical history, and brief physical exam of the ears conducted by site clinician; time from Screening Visit to Clinic Visit 1 will be no longer than 3 weeks
- ***Clinic Visit 1 (~1.5 hour):*** examination of the ears by an audiologist who may remove ear wax if deemed required and consented to by participants, bone conduction audiometry, tympanometry, Pure Tone Audiometry (air conduction audiometry), enrollment, and baseline hearing assist software settings
- ***Home Interval 1 (3-8 days; begins on same day as Clinic Visit 1):*** observations of baseline hearing assist software settings during participant's daily activities, Participants have the option to make setting adjustments during this interval for listening needs and/or to avoid discomfort, regular charging of study devices, and encouraged daily use of devices. Participants who have no evidence of at least daily use for several days will be contacted by study staff to assess for troubleshooting needs. Minimum expected wear time is at least 30 minutes per day for at least 3 days during this interval.
- ***Clinic Visit 2 (~1.5 hours):*** examination of the ears by an audiologist who may remove ear wax if deemed required and consented to by participants, hearing assist software setting fine-tuning, Real Ear measures, and SIN objective hearing test
- ***Home Interval 2 (14-22 days; begins on same day as Clinic Visit 2):*** fine-tuning of hearing aid settings during participant's daily activities, regular charging of study devices, and encouraged daily use of devices. Participants who have no evidence of at least daily use for several days will be contacted by study staff to assess for troubleshooting needs. Minimum expected wear time is at least 30 minutes per day for at least 14 days during this interval.
- ***Clinic Visit 3 (~1-2 hours):*** examination of the ears by an audiologist who may remove ear wax if deemed required and consented to by participants, IOI-HA survey, Real Ear measures, SIN objective hearing test, and end of study items

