7.4. Reporting

7.4.1. Adverse Events

Throughout the entire study period, once participants have signed the ICF, the PI and/or designee(s) will evaluate participants at each study visit, record all AEs (whether or not they are considered to be related to the study procedures), and determine if any AEs are device- or study-related. Signs and symptoms of each AE should be described in detail and include approximate onset time and date, approximate offset time and date, description of event, severity, relationship to study procedures, action taken, outcome,

and (if applicable) the PI's opinion of the causal relationship between the event and the study procedures.

AEs will be collected as reported by participants and reported as observed by study staff. All AEs will be documented on the AE form and will be reported within 10 working days of learning of the event by Study Staff to the Sponsor. If deemed necessary by the Sponsor, the CRO or Study Staff will notify the Institutional Review Board (IRB).

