9.2. Data Analysis

In general, descriptive statistics (e.g., N, Mean, Std. Dev., Min, Max) for continuous data types and frequencies for categorical data types will be displayed. All analyses will be performed with SAS [REDACTED] and/or R [REDACTED]. Analysis results will be presented separately for each of the two randomized groups and overall as appropriate.

Subject accountability (number of enrolled, withdrawn (and reasons), and complete), demographic and baseline characteristics (i.e., age, sex at birth, race, ethnicity, height, weight, BMI, etc.) and medical history will all be summarized using the Full Analysis Set. Baseline ear measures (i.e., PTA, bone conduction, and tympanometry) will be summarized separately for each ear.

All adverse events will be summarized in terms of event type, severity, and relationship to device/study procedures. Serious adverse events will also be summarized. The overall incidence (number of study participants and number of events) will be presented as both frequency counts and percentages.

Details of the efficacy analyses including the primary endpoint and additional exploratory analyses are presented below.

The full analysis set will be used as the pivotal analysis set to test the primary endpoint hypothesis. The methodology and missing data mechanism assumptions will be described in the study Statistical Analysis Plan (SAP). The null hypothesis, H_0 , will be rejected and the Self-Fit group will be considered non-inferior to the Pro-Fit group if the one-sided p-value for this test is $p < 0.025$ or equivalently, if the one-sided upper 97.5% confidence bound for the difference (Pro-Fit – Self-Fit) of the two group means is no more than 3. The primary endpoint analysis will also be performed on the Per Protocol and Complete Cases Analysis Sets as supportive analyses.

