After a particular hearing loss recruitment category has been filled, subjects identified at screening within that category may be dispositioned prior to randomization. Information collected at the screening visit and clinic visit 1 (e.g., informed consent, medical history, demographics, otoscopy exam, perceived hearing loss questionnaire, eligibility criteria, and pure tone audiometry, tympanometry, and bone conduction) for these subjects will be presented in the listings but will not be included in any of the full analysis set analyses because they were not randomized.

5. Study Procedures

Participants will have a screening visit and up to three scheduled clinic visits interspersed by two home intervals. The participants enrolled into the sub-study cohort will follow similar study procedures:

- Screening Visit (~2 hours): informed consent, potential Pure Tone Audiometry (air conduction audiometry), medical history, and brief physical exam of the ears conducted by site clinician; time from Screening Visit to Clinical Visit 1 will be no longer than 3 weeks

[figure not shown]

- Clinic Visit 1 (~1.5 hour): examination of the ears by an audiologist who may remove ear wax if deemed required and consented to by participants, bone conduction audiometry, tympanometry, Pure Tone Audiometry (air conduction audiometry), enrollment, and baseline hearing assist software settings
- Home Interval 1 (3-8 days; begins on same day as Clinic Visit 1): at-home observations of baseline hearing assist software settings during participant's daily activities. Participants have the option to make setting adjustments during this interval for listening needs and/or to avoid discomfort, regular charging of study devices, and encouraged daily use of devices. Participants who have no evidence of at least daily use for several days will be contacted by study staff to assess for troubleshooting needs. Minimum expected wear time is at least 30 minutes per day for at least 3 days during this interval.
- Clinic Visit 2 (~1.5 hours): examination of the ears by an audiologist who may remove ear wax if deemed required and consented to by participants, hearing assist software setting fine-tuning, Real Ear measures, and SIN objective hearing test

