7.6. Interim Analyses

There are no interim analyses planned in this study.

8. Analysis Sets

The following analysis sets are defined for this study.

Eligible Analysis Set: All subjects who sign informed consent and meet eligibility criteria for the CV portion of the study. Some of these subjects may not have been randomized if the hearing loss recruitment category is already filled.

Full Analysis Set (FAS): All subjects who sign informed consent, meet eligibility criteria, and are enrolled and randomized into the CV portion of the study. This analysis set will be used for the primary endpoint analysis and to summarize subject accountability, protocol deviations, demographic and baseline characteristics, and adverse event data. Subjects in this analysis set will be analyzed “as randomized”.

Per Protocol Analysis Set (PPS): All subjects who meet predetermined minimum data usability criteria, and who do not have any major protocol deviations that would necessitate exclusion from analysis. Subjects in this analysis set will be analyzed “as treated”. This analysis set will be used as a supportive analysis of the primary endpoint. Subjects in the PP analysis set must meet the following two minimum usability criteria:

- 1) >10 minutes of Airpod wear for at least 1 day during home interval 1 AND
- 2) >10 minutes/day of Airpod wear for at least 7 days during home interval 2

The minimum wear times are justified to obtain the most accurate assessment of hearing aid benefit as measured by the IOI-HA questionnaire.

Complete Cases Analysis Set (CCAS): All subjects who have complete data for the efficacy endpoints of IOI-HA, QuickSIN, or Real Ear Measures. This analysis set will be used as a supportive analysis of the primary endpoint.

9. Analysis Approach

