9.8. Safety Analyses

All adverse events will be recorded throughout the entire study period, whether they are considered to be related to the study procedures or not. Signs and symptoms of each AE will be described in detail: date of event, description of event, severity, relationship to study procedures, action taken and outcome. Adverse events will be collected as spontaneously reported by the subjects.

Adverse events will be coded using MedDRA v24.1. The number of any adverse events and the number and percentage of subjects reporting each type of adverse event will be presented by preferred term. Multiple occurrences of the same event reported by the same subject will be counted only once.

Adverse event summaries (number of events and incidence) will be presented for:

- All adverse events
- Serious adverse events (SAEs)
- Study procedure related adverse events
- Severe adverse events

The intensity of an AE will be categorized as follows:

- Mild: Events that are transient, easily tolerated by the participant, and does not affect the participant's daily activities
- Moderate: Events that cause the participant discomfort and interrupts the participant's usual daily activities. May require treatment but not extended hospitalization for the participant.
- Severe: Events that are incapacitating, causing inability to do work or usual activities; signs and symptoms may require medical evaluation and/or treatment, and may require additional prolonged hospitalization

Causal relationship assessment to study procedures is required for purposes of reporting AEs. To promote consistency, the following guidelines should be taken into consideration along with good clinical and scientific judgment when determining the relationship of study procedures to an AE:

- Probably Related: There is a strong temporal relationship to the study or device, and an alternative etiology for the AE is unlikely.
- Possibly Related: The event is not readily explained by the participant's medical condition, concomitant therapy, or other causes, and there is a plausible temporal relationship between the event and participation in study procedures.

- Probably Not Related: An event, for which an alternative explanation is more likely (e.g., concomitant medications or ongoing medical conditions) or the temporal relationship to study procedures and/or exposure suggests that a causal relationship is unlikely.

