Table 14.2.1.3	Logistic Regression Analysis to Evaluate Probability of Missingness – Per Protocol Analysis Set
Table 14.2.1.4	Primary Endpoint Analysis of IOI-HA – Per Protocol Analysis Set
Table 14.2.1.5	Primary Endpoint Analysis of IOI-HA – Complete Cases Analysis Set
Table 14.2.1.6	IOI-HA Item Summary – Complete Cases Analysis Set
Table 14.2.2	QuickSIN Results– Complete Cases Analysis Set
Table 14.2.3.1.1	Real Ear Measures Summary at 50 dB SPL (Clinic Visit 2) – Complete Cases Analysis Set
Table 14.2.3.1.2	Real Ear Measures Summary at 50 dB SPL (Clinic Visit 3) – Complete Cases Analysis Set
Table 14.2.3.2.1	Real Ear Measures Summary at 65 dB SPL (Clinic Visit 2)– Complete Cases Analysis Set
Table 14.2.3.2.2	Real Ear Measures Summary at 65 dB SPL (Clinic Visit 3)– Complete Cases Analysis Set
Table 14.2.3.3.1	Real Ear Measures Summary at 80 dB SPL (Clinic Visit 2) – Complete Cases Analysis Set
Table 14.2.3.3.2	Real Ear Measures Summary at 80 dB SPL (Clinic Visit 3) – Complete Cases Analysis Set
Table 14.2.4.1	Mean Absolute Difference of Real Ear Measures from NAL-NL2 Targets at 50 dB SPL– Complete Cases Analysis Set
Table 14.2.4.2	Mean Absolute Difference of Real Ear Measures from NAL-NL2 Targets at 65 dB SPL
Table 14.2.4.3	Mean Absolute Difference of Real Ear Measures from NAL-NL2 Targets at 80 dB SPL

Table 14.3.1.1	Summary of Adverse Events – Full Analysis Set
Table 14.3.1.2	All Adverse Events Sorted Alphabetically – Full Analysis Set
Table 14.3.1.3	Serious Adverse Events – Full Analysis Set
Table 14.3.1.4	Adverse Events Possibly or Probably Related to Study Procedures – Full Analysis Set
Table 14.3.1.5	Adverse Events Rated Severe in Intensity – Full Analysis Set

List of Listings

Listing 16.2.1	Discontinued Patients
Listing 16.2.2.1	Protocol Deviations: Type and Description
Listing 16.2.2.2	Protocol Deviations: Severity and Actions Taken
Listing 16.2.4.1	Baseline Demographics
Listing 16.2.6.1	IOI-HA Responses
Listing 16.2.7.1	Adverse Events: Description and Timing
Listing 16.2.7.2	Adverse Events: Severity and Relationship
Listing 16.2.7.3	Adverse Events: Actions and Outcomes
Listing 16.2.9.1	Subject Eligibility and Enrollment
Listing 16.2.9.2	Perceived Hearing Loss Questionnaire
Listing 16.2.9.3	Subject Disposition
Listing 16.2.9.4	Medical History
Listing 16.2.9.5.1	Otoscopy Examination Results
Listing 16.2.9.5.2	Otoscopy Examination Additional Information
Listing 16.2.9.6	Clinical Visits Summary
Listing 16.2.9.7.1	Pure Tone Reference Audiometry (1)

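### AEs are collected from consent but summarised only in randomised participants with no cut at first fitting, so pre-device and device-period events are mixed and events in unrandomised participants reach no summary table

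*SAP*

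**What the plan says.** **Collection.** Protocol 7.4.1 starts AE recording early: "Throughout the entire study period, once participants have signed the ICF, the PI and/or designee(s) will evaluate participants at each study visit". SAP 9.8 agrees: "All adverse events will be recorded throughout the entire study period, whether they are considered to be related to the study procedures or not". Protocol 3.2 places informed consent at the Screening Visit.

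**First device exposure.** Protocol 1.13 provides the headphones and smartphone at Clinic Visit 1. Protocol 3.2 limits the gap before that visit: "time from Screening Visit to Clinic Visit 1 will be no longer than 3 weeks".

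**Analysis set.** SAP 8 and Protocol 9.3 assign AE data to the FAS, which contains only eligible, enrolled and randomised participants. In the SAP the set is used "to summarize subject accountability, protocol deviations, demographic and baseline characteristics, and adverse event data". All five AE tables in SAP 13 (14.3.1.1 to 14.3.1.5) carry that set, beginning with "Summary of Adverse Events – Full Analysis Set".

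**Subdivision.** SAP 9.8 divides AEs by seriousness, relation to study procedures and severity. Neither document defines a device-emergent AE or a period before and after fitting. SAP 9.8 also counts repeat occurrences of the same event in one participant only once.

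**Unrandomised participants.** SAP 4 allows eligible people to be left unrandomised when their hearing-loss category is full. Their screening and Clinic Visit 1 data go to listings but "will not be included in any of the full analysis set analyses because they were not randomized".

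**The concern.** A reader will take an AE table with Self-Fit and Pro-Fit columns as a description of what happened under each fitting. As planned, each column also holds illness that began before the participant had a device or an assignment. This raises the apparent incidence in both arms and pulls a relative comparison towards no difference.

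The count-once rule adds to this. If a participant has an event before fitting and the same event again afterwards, the incidence count records one participant once, and the recurrence under the device cannot be seen there.

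Separately, the population in which AEs are collected (everyone who consents) is wider than the population in which they are summarised (everyone randomised). For the difference there is neither a table nor a denominator.

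**Working it through.** **1. Device period, checked against the plan's own figure.** Home Interval 1 is 3 to 8 days and Home Interval 2 is 14 to 22 days (Protocol 3.2). The sum is 3 + 14 = 17 to 8 + 22 = 30 elapsed days, or 18 to 31 days counted inclusively. This reproduces the 18 to 31 days of participation in Protocol 1.14.

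**2. Pre-device period.** From consent at screening to Clinic Visit 1: 0 to 21 days (Protocol 3.2). The documents give the maximum, not a typical value.

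**3. Share of AE calendar time before the device.** Share = pre / (pre + post).

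| Days before fitting | Post = 30 days | Post = 17 days |
|---|---|---|
| 0 | 0% | 0% |
| 7 | 7/37 = 19% | 7/24 = 29% |
| 14 | 14/44 = 32% | 14/31 = 45% |
| 21 | 21/51 = 41% | 21/38 = 55% |

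**4. Effect on event rates (illustration).** Assume a constant background rate and a true rate ratio of 2 after fitting. The tabulated ratio is (pre + 2 × post) / (pre + post). With a 21-day lead-in:
- post = 30: (21 + 60)/51 = 1.59
- post = 17: (21 + 34)/38 = 1.45

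In the arm with the background rate, the expected number of events rises by a factor of (pre + post)/post: 51/30 = 1.70 or 38/17 = 2.24.

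**5. Effect on the percentage of participants with an event (illustration).** Assume true risks after fitting of 10% and 20%, constant hazards, and a pre-fitting hazard equal to that of the 10% arm. The tabulated risks are 1 − 0.90^((pre + post)/post) and 1 − 0.90^(pre/post) × 0.80. With a 21-day lead-in:
- post = 30: 16.4% and 25.7%; difference 9.3 points, ratio 1.57
- post = 17: 21.0% and 29.8%; difference 8.8 points, ratio 1.42

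The ratio shrinks clearly, while the absolute difference moves only from 10 to about 9 points. These are worst-case lead-ins with assumed risks; the documents give no AE rates.

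**6. Direction.** Randomisation follows the enrolment process (Protocol 4.7), and enrolment comes after the examinations at Clinic Visit 1 (Protocol 3.2). Events before fitting therefore precede assignment and balance between arms in expectation.

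**7. Coverage of unrandomised participants.** No AE table uses the Eligible Analysis Set or all consented participants. Listings 16.2.7.1 to 16.2.7.3 name no analysis set. The SAP 4 sentence on listings does not mention AEs in its examples, and it does not cover people who consent and then fail eligibility. Their number is not stated.

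**The case against.** Three stronger readings are tempting, and the documents do not support them.

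**Selective loss of procedure-related events.** A reader might infer that someone harmed by the ear examination or wax removal at Clinic Visit 1 becomes ineligible and so disappears from the table because of that harm. Protocol 7.3.4 says that injury from ear exams or wax removal, cerumen impaction, abnormal audiograms and hearing symptoms are not to be regarded as AEs. Most foreseeable events of this kind would be in no AE table whatever the analysis set. Moreover, SAP 4 describes eligible people left out because a recruitment category was full, a reason unrelated to any event.

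**Events lost from the report.** Absence is shown only for the summary tables. The listings may carry these events, and serious events still go to the sponsor within 24 hours and to the IRB within 10 working days (Protocol 7.4.2). A listing, however, gives no incidence or denominator.

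**A contradiction inside the protocol.** Protocol 9.2 promises "All adverse events will be summarized in terms of event type, severity, and relationship to device/study procedures", but Protocol 9.3 then assigns AE data to the FAS. Read together, the two are a restriction, not a conflict.

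It can also be said that the AE summaries are descriptive, that causality is judged against study procedures with a separate table for related events, and that the columns by arm come only from a general sentence in Protocol 9.2, since SAP 9.8 names none. All of this stands. It limits the weight of the point but does not supply an onset cut-off.

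**Conclusion.** The point holds as a gap in the safety presentation. Pre-device events enter the same tables as device-period events, and unrandomised participants' AEs are in no summary table. The mixing takes up 0 to 55% of a participant's AE calendar time. The upper part of that range applies only to someone who uses all 21 days, and it is a share of time, not of events.

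The effect is inflated incidence per arm and dilution of a relative difference, with no directional bias. The volume is probably small, given the exclusions in Protocol 7.3.4; what remains is mainly general medical events over at most three weeks. The primary endpoint is untouched. The change is worth making because it is cheap, not because a conclusion of the trial depends on it.

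The dilution figures rest on constant hazards and assumed risks. The pre-fitting share rests only on the visit windows.

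**What to change.** **In SAP 9.8:**
1. Define a device-emergent AE as one with onset or worsening at or after first fitting at Clinic Visit 1. For events on that day, use the approximate onset time required by Protocol 7.4.1, and state a default where the time is missing.
2. Re-cut Tables 14.3.1.1 to 14.3.1.5 to show device-emergent AEs by randomised arm in the FAS, and state the columns.
3. Apply the count-once rule within each period, so that a recurrence after fitting is counted.
4. Add one overall table of AEs and serious AEs from consent to first fitting or exit, for all consented Clinical Validation participants, randomised or not.

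**In SAP 8:** define the all-consented denominator for that table. The broadest existing set, the Eligible Analysis Set, requires eligibility and is too narrow.

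**Cost.** Five tables are re-cut, one table and one denominator are added, and onset time must be carried into the analysis data, because SAP 9.8 names only the date of the event. No new data are collected.

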9.1. Subject Accountability

A summary of the number of eligible subjects, randomized subjects, withdrawn subjects, and completers will be presented by randomized treatment group (if applicable) and overall. Reasons for withdrawal will be summarized according to the following categories:

- Adverse Event
- Loss of Study Provided Materials
- Protocol Violation
- Does Not Meet Inclusion Exclusion Criteria After Enrollment

- Withdrawal of Consent by Subject
- PI Discretion
- Termination of Study
- Lost to Follow-up
- Other

Results of the perceived hearing loss questionnaire will also be summarized descriptively.

9.2. Device Measurement Accountability

A summary table will be reported which presents total duration of device wear time (hours) across home intervals 1 and 2 and the percentage of days worn where the audio settings were changed. These results will be presented overall and by randomized treatment group. Device dispensing and return information will be presented in the listings.

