- Home Interval 2 (14-22 days; begins on same day as Clinic Visit 2): at-home fine-tuning of hearing aid settings during participant's daily activities, regular charging of study devices, and encouraged daily use of devices. Participants who have no evidence of at least daily use for several days will be contacted by study staff to assess for troubleshooting needs. Minimum expected wear time is at least 30 minutes per day for at least 14 days during this interval.
- Clinic Visit 3 (~1-2 hours): examination of the ears by an audiologist who may remove ear wax if deemed required and consented to by participants, IOI-HA survey[3], Real Ear Measures, SIN objective hearing test, and end of study items
- Participants may be asked to complete additional study procedures due to unforeseen circumstances such as replacing study equipment due to loss, theft, or damage.

Figure 5.1 depicts a diagram of study assessments and procedures.

Figure 5.1: Diagram of Study Assessments and Procedures

6. Study Endpoints

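### Does reporting wear only as total hours (SAP 9.2) leave a gap that needs a plan change?

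*SAP*

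**What the plan says.** SAP 9.2 plans one table of device use, by arm and overall, with two measures: "total duration of device wear time (hours) across home intervals 1 and 2" and "the percentage of days worn where the audio settings were changed". The second takes days worn as its denominator, so it describes tuning behaviour and not adherence. SAP 13 lists the table as 14.1.4, on the Full Analysis Set.

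Wear thresholds appear in two other places.

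- SAP 5 (and Protocol 3.2) states an expectation for each home interval. For interval 1, which may last 3 to 8 days: "Minimum expected wear time is at least 30 minutes per day for at least 3 days during this interval". For interval 2, which may last 14 to 22 days: "Minimum expected wear time is at least 30 minutes per day for at least 14 days during this interval".
- SAP 8 sets two usability criteria for the Per Protocol set: ">10 minutes of Airpod wear for at least 1 day during home interval 1 AND" ">10 minutes/day of Airpod wear for at least 7 days during home interval 2".

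Neither document says that the number meeting the 30-minute expectation will be tabulated.

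**The concern.** Both rules count days at a daily threshold, one interval at a time, while the planned measure pools hours over both intervals. A reader of Table 14.1.4 cannot recover how many participants in each arm used the device as expected. The total is also not divided by interval length, so it mixes daily use with visit scheduling.

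This could matter because the trial is an unblinded non-inferiority comparison on a questionnaire about hearing-aid benefit. If one arm used the device much less, or if both used it very little, the IOI-HA comparison would be harder to interpret. A total in hours might look balanced when adherence was not, or look unbalanced only because visits were booked differently.

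The other listed outputs do not clearly close the gap. Table 14.1.2 should give the Per Protocol count, but that set also removes major deviations. Listing 16.2.9.9 may hold daily wear, but it is a listing and not a summary by arm.

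**Working it through.** **Interval lengths.** The windows in SAP 5 sum to 3 + 14 = 17 days at the shortest and 8 + 22 = 30 at the longest. Counting the first visit day gives 18 to 31, which reproduces the participation length in Protocol 1.14.

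**Do total hours determine either rule?** No.

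- SAP 5 expectation: smallest qualifying total (30 × 3 + 30 × 14)/60 = 510/60 = 8.5 h. Yet 1 h on 3 interval 1 days and 13 interval 2 days gives 16 h and fails.
- Per Protocol criteria: smallest qualifying total just over (10 × 1 + 10 × 7)/60 = 80/60 = 1.33 h. Yet 1 h on 8 interval 1 days and 6 interval 2 days gives 14 h and fails.

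The implication does run one way: a total below 8.5 h shows that the SAP 5 expectation was missed. Very low use in both arms would therefore be visible in the planned table.

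**Can interval length distort the arm comparison?** For two individuals, yes: 30 minutes every day gives 0.5 × 17 = 8.5 h or 0.5 × 30 = 15 h, and 15/8.5 − 1 = 76%. The table, however, compares randomised arms of 56 (SAP 7.1). The 95% chance range for the difference in mean length is ±1.96 × SD × √(2/56). The documents give no distribution of lengths, so two are assumed, both with mean 5.5 + 18 = 23.5 days.

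- Uniform within each window: variance 2.917 + 6.667 = 9.583, SD 3.10, range ±1.15 days, or 1.15/23.5 = 4.9%.
- Every length at a window limit: SD √(2.5² + 4²) = 4.72, range ±1.75 days, or 7.4%.

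**Can equal mean hours hide unequal adherence?** The wear patterns here are assumed. Suppose one arm wears the device on 95% of days for 60 minutes, and the other on 70% of days for 60 × 0.95/0.70 = 81.4 minutes. Worn days are binomial. The share meeting SAP 5 is P(Bin(L1, q) ≥ 3) × P(Bin(L2, q) ≥ 14). The SD of total hours is (m/60) × √[(L1 + L2) q (1 − q)], where m is minutes per worn day.

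| Interval lengths (days) | Mean hours, both arms | Meeting SAP 5 | SD of hours |
|---|---|---|---|
| 3 and 14 | 16.15 | 41.8% vs 0.2% | 0.90 vs 2.56 |
| 5 and 18 | 21.85 | 99.7% vs 27.8% | 1.05 vs 2.98 |
| 8 and 22 | 28.5 | 100% vs 80.4% | 1.19 vs 3.41 |

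The means hide the difference, but the spread does not: the SDs differ nearly threefold in each row. Protocol 9.2 says continuous data will in general be shown with N, mean, SD, minimum and maximum.

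A cruder case behaves the same way. Over 24 days, 56 people at 0.6 h/day average 14.4 h. So do 28 at 1.1 h/day with 28 at 0.1 h/day, since (26.4 + 2.4)/2 = 14.4. The second arm's minimum is 2.4 h against 14.4 h in the first.

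**Is a count less sensitive to scheduling?** No. In the table above, the same 95%-of-days user goes from 41.8% to 100% meeting the expectation between the shortest and longest intervals, while mean hours rise by 28.5/16.15 − 1 = 76%. A 14-day interval 2 allows no missed day; a 22-day one allows eight.

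**The case for a change.** The strongest case for a change is that the mismatch follows from the definitions and needs no assumption. In an unblinded non-inferiority trial a reader should be able to see that the device was used, and the Per Protocol floor is low: just clearing it takes about 80 of the 510 expected minutes, or 16%. The remedy would be a few rows from data already needed, and naming them in advance avoids choosing an adherence measure after seeing results.

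Part of this stands. No listed summary table shows, by arm, how many met the 30-minute expectation, and a reader may reasonably want that.

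The rest is weaker. The sentence in SAP 8 that links wear to accurate measurement of benefit justifies the 10-minute criteria, not the 30-minute expectation, and the plan acts on those criteria with a supportive Per Protocol analysis of the primary endpoint (SAP 9.5). Daily use is also item 1 of the IOI-HA, and Table 14.2.1.6 summarises the items, though by self-report and in complete cases only. The worry about a post hoc choice is limited, because the 30-minute thresholds and day counts are already fixed in SAP 5.

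**Conclusion.** The observation is correct but calls for no change to the plan. SAP 9.2 leaves a descriptive gap that analysts can fill when the tables are built. The Per Protocol criteria and the days-worn denominator already require wear by day, and the study app records estimated wear (Protocol 8.1.2). Rows for interval length, wear per day and the number meeting the SAP 5 expectation would be an optional courtesy to readers, best read side by side.

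No stated rule gives a wrong result. The primary test on the Full Analysis Set, the Per Protocol analysis and the membership of every analysis set stay the same with or without those rows. The two wear rules serve different purposes and do not conflict.

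The effect on arm balance is modest: about 4.9% to 7.4% of mean interval length by chance. This rests on the assumed length distributions, on 56 per arm, and on visit timing and dropout not differing by arm. If they did differ, total hours would need to be read with interval length alongside. The reassurance from the spread assumes that the general descriptive statistics in Protocol 9.2 are applied to this table.
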